6.4. PARTICIPANT RECRUITMENT AND SCREENING

Will participants be screened?	YES
If yes, what data will be collected? (NB, if participant is not eligible, will data collected be destroyed or kept?) This should be mentioned in PIS/CF)	Age, ability to give consent, in shared care or willing to enter shared care arrangement, language
Who will make initial contact with participants?	Care Coordinators and Shared Care Clinicians (“Clinicians”) at participating mental health services will verbally introduce the study to the consumer during a consultation.
Who will perform the consent process? How will this be carried out?	A research officer will explain the contents of the participant information form using a script (Appendix

Will participants be screened?	YES
If yes, what data will be collected? (NB, if participant is not eligible, will data collected be destroyed or kept?) This should be mentioned in PIS/CF)	Age, ability to give consent, in shared care or willing to enter shared care arrangement, language
Who will make initial contact with participants?	Care Coordinators and Shared Care Clinicians (“Clinicians”) at participating mental health services will verbally introduce the study to the consumer during a consultation.
	10.6) and answer any questions the consumer might have.
Will participants be consented verbally/explicitly/using eConsent?	Explicit or verbal
Will participants be given 24 hours to consider participating?	YES
Review of existing databases or databanks (please identify the database/databank and the custodian)	SLHD hospital records(SLHD), HealtheNet (eMR SLHD), ICOD (New South Wales Ministry of Health), GP records (private practice). De-identified data will be stored in ReDCap of the SLHD

Will participants be screened?	YES
If yes, what data will be collected? (NB, if participant is not eligible, will data collected be destroyed or kept?) This should be mentioned in PIS/CF)	Age, ability to give consent, in shared care or willing to enter shared care arrangement, language
Who will make initial contact with participants?	Care Coordinators and Shared Care Clinicians (“Clinicians”) at participating mental health services will verbally introduce the study to the consumer during a consultation.
Review of clinic files (please include who will be reviewing these files, for example a research coordinator).	LHD mental health clinic files will not be reviewed by the research team.
Advertisements (please include where the advertisement will be placed for example, in a newspaper, poster in a clinic or hospital foyer, radio announcements, website etc.)	A recruitment advertisement will be placed in clinic waiting rooms, inviting consumers to contact a member of the clinical team to discuss the study (Appendix 5)
Information Letter to Medical practitioners	YES (Appendix 10.2)
Explain how potential participants will be screened for the study	Clinician will assess suitability for study criteria

Will participants be screened?	YES
If yes, what data will be collected? (NB, if participant is not eligible, will data collected be destroyed or kept?) This should be mentioned in PIS/CF)	Age, ability to give consent, in shared care or willing to enter shared care arrangement, language
Who will make initial contact with participants?	Care Coordinators and Shared Care Clinicians (“Clinicians”) at participating mental health services will verbally introduce the study to the consumer during a consultation.
Any other potential recruitment methods.	-

6.5. PARTICIPANT ENROLMENT

Potential participants will be enrolled into the study after the informed consent process has been completed and the participant has been assessed to meet all the inclusion criteria and none of the exclusion criteria. Study participants will receive a study enrolment number and this will be documented on all study documents.

6.6. INFORMATION AND CONSENT

All potential study participants will be provided with a comprehensive information sheet about the research (Appendix 8) and they will be required to provide written consent (Appendix 11) (or verbal consent if they have literacy difficulties Appendix 11.2) before being able to participate in the study.

SLHD templates have been used to develop the information and consent forms.

6.7 WAIVER OF CONSENT

Not applicable

6.8. END OF STUDY TREATMENT/WITHDRAWAL PROCEDURE

Participants may withdraw from the study at any time. If they decide to withdraw from this research project, they will need to notify a member of the research team (details provided in the participant information sheet) and they will be asked to complete withdrawal form. If they do not want to complete a withdrawal form, the research team will try to ascertain the reason for withdrawal, whether there are any problems that need to be followed up, and whether the existing data and secondary data can be used.

Withdrawn participants will not be replaced.

After the intervention, GPs who wish to continue to use this online shared care plan will need to pay an annual fee (currently estimated to be \$60 per practice per annum). Alternatively, the online shared care plan can be exported as a text document (pdf format) and used in the same way that existing care plans are used by GPs and mental health services and saved within their medical record software.

6.9. PARTICIPANT WITHDRAWAL

Participants may withdraw from the study for the following reasons: participant has chosen to withdraw from the study, protocol violation, or participant has experienced an adverse event.

If a participant withdraws from the study, the research team will not collect additional health information about that person, although information already collected will be retained to ensure that the results of the research project can be measured properly and to comply with law. If the participant does not want their data to be included, they must tell the researchers when they withdraw from the project.

The consumer will be coded as 'withdrawn – existing data to be used 'or 'withdrawn – existing data not to be used'.

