
Study Procedure
	
 1.SLHD Adult Community Mental Health 'Core' Teams will be randomised to – 1 of Canterbury or Croydon and 1 of Camperdown or Marrickville will be randomly allocated to the intervention group and the other will receive delayed intervention 2.500 People with severe mental illness (PWSMI) who have contact with these teams and who are identified as suitable by the Core team staff member who is their care coordinator during routine visits will be given written information about the study. With the consumer’s permission, care coordinators will provide the research team with contact details of consumers who are interested in participating in the study. 3.A research officer will contact these potential participants to explain the study, answer any questions, and obtain informed consent. 4.Participant consumers will be asked to approach their GP to be part of the project OR consent to the research team doing so on their behalf to recruit GPs to the study. 5.If GPs provide consent to participate in the study, they and their patient are enrolled in the study and an appointment is made to install the INCA shared care software in the GP practice’s computer and arrangements will be made to train the GP in its use and a baseline survey is conducted with the consumers and their shared-care GPs. 6.Consumers in the intervention group will have their physical health care coordinated through an online shared care plan. 7.Consumers in the comparison group will receive usual care. 8.If GPs withdrew consent to participate in the study, their patient will remain enrolled in the study and will be able to participate in a repeat interview 3 months after their reported usual shared care. 9.Consumer and GP participants will participate in a repeat interview 3 months after their reported usual shared care. If any consumer does not have a shared care appointment/follow-up since baseline, they will be invited to participate in the repeated interview three months after 30 June 2023 (i.e., 3 months after the deadline for the intervention to be implemented). 10.With consent and approval, relevant health service use and clinical data will be extracted from medical records held by GPs, datasets held by SLHD, HealthNet (including MBS/PBS items), and the NSW Ministry of Health (ICOD). 11.A subset of consumers will be invited to participate in a qualitative interview after 3 months of their reported usual shared care. 12.A subset of SLHD mental health clinicians (Care Coordinators and shared care clinicians) and GPs will be interviewed after the intervention period.

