8.2. PROVIDE A DETAILED ANALYSIS PLAN

Quantitative analysis

The fidelity and tailoring of the intervention to participants' needs will be assessed by analysing records, provider and consumer interviews 3 months after their usual shared care appointments. We will compare outcomes over 3 months after intervention between SHAReD intervention and comparison groups with linear or generalised multi-level mixed models including age, sex and key independent variables that are found to be significantly different between groups at baseline. Intra-class correlations will be calculated to compare the amount of variance associated with design features such as individual participants nested within care coordinators who are nested within community mental health teams, and those same participants are also nested within GPs who could also be nested within medical centres, before selecting random effects for these statistical models. As well as an analysis of completers (defined as those consumers, care coordinator and GP who

consented and are engaged in shared care), an intention to treat (ITT) analysis will also be included for this project. For the ITT analysis, those who drop out of the study (defined as consumers who were discharged of shared care or who withdrew consent) will be treated using a variety of sensitivity analyses including multiple imputation for the missing values on key measures resulting from them dropping out of the study. Sensitivity analyses will assess unmeasured variation.

Qualitative analyses

This will evaluate the experience of participants, carers and providers, barriers to implementation, conditions for sustainability and translation. Qualitative data will be managed and coded using NVivo 11 analysis software (QSR International). Two researchers will review each transcript and develop coding aligned with the Theoretical Domains Framework and Normalisation Process Theory.^{25,26} Coding will be predominantly deductive but inductive coding will also be applied to detect new and emerging themes.

Data combining and cost analyses

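### Section 6.9 lets a protocol violation or an adverse event end a consumer's data collection, which fits neither the ITT analysis nor the protocol's own retention rules

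*Protocol*

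**What the plan says.** Protocol section 6.9 lists the reasons for leaving the study: "participant has chosen to withdraw from the study, protocol violation, or participant has experienced an adverse event". The consequence is the same for all three: "If a participant withdraws from the study, the research team will not collect additional health information about that person". Data already held are kept unless the participant objects, and both status codes concern existing data only.

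Section 6.8 says that withdrawn participants are not replaced. Where no withdrawal form is completed, the team tries to find out "whether the existing data and secondary data can be used". Section 6.9 does not carry that question over.

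Section 8.2 plans an ITT analysis beside a completers analysis. Its drop-outs are "defined as consumers who were discharged of shared care or who withdrew consent", and they are handled by sensitivity analyses that include multiple imputation.

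Other parts of the protocol take care to retain people. Under item 8 of the synopsis study procedure, when a GP withdraws, "their patient will remain enrolled in the study". Item 9 and sections 4.5, 5.3 and 9.2 keep further groups in follow-up.

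**The concern.** An ITT analysis needs outcomes on everyone in the allocated arm, whatever happened after allocation. Only a participant's refusal of further data collection should end it. Section 6.9 adds two reasons that are not consent decisions and attaches the same complete stop to them. If the team uses them, outcomes that could still be obtained are lost for people selected by what happened to them during the trial. If that happens more in one arm than in the other, the ITT comparison is biased as well as less precise.

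**Working it through.** **1. Which situations end data collection.**

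| Situation | Data collection continues? | Where |
|---|---|---|
| GP withdraws consent | Yes | Synopsis, item 8 |
| No shared care appointment since baseline | Yes, survey timed from 30 June 2023 | Synopsis, item 9; 4.5; 9.2 |
| GP declines, comparison group | Yes, expressly for ITT | 4.5 |
| GP does not take part | Yes | 5.3, item 9 |
| Admitted to hospital after recruitment | Assessment after discharge, if the consumer agrees | 5.3, item 7 |
| Consumer withdraws consent | No | 6.9; within the 8.2 drop-out definition |
| Protocol violation | Withdrawal permitted, then no | 6.9; not in the 8.2 definition |
| Adverse event | Withdrawal permitted, then no | 6.9; not in the 8.2 definition |

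The last two rows are the gap. They are withdrawals by reason rather than by consent, and 8.2 does not define how the ITT analysis treats them.

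**2. What would be lost.** Table 9 takes screening and prescribing from records for May to October 2023, and advice or referral from the repeat survey. ED use, admissions and GP visits use the same six months. A consumer withdrawn before these data are collected has baseline data but no follow-up outcome.

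**3. Whether the arms are treated alike.** Under section 6.3 the incident system covers all teams. The weekly reports are then searched for enrolled consumers in the intervention arm, and only GPs in that arm are asked to notify events. No matching step is described for usual care. An adverse event known to the trial, and so available as a reason under 6.9, would therefore be found mainly in one arm.

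**4. What can be said about size.** Section 6.3 gives about ten adverse events a week across five teams. With an even spread, two teams have 10 × 2/5 = 4 a week, or 4 × 26 = 104 over a six-month window. These are events, not people, among all clients of the two teams. The protocol does not give the share among enrolled consumers, or how many would be withdrawn. It gives no rate at all for protocol violations.

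The form of the bias is simple. If a fraction w of one arm is removed, with success rate q among those removed and r among those kept, the arm's rate is overstated by

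r − [(1 − w)r + wq] = w(r − q).

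This is zero if those removed do as well as those kept (q = r). For scale only, with r = 0.50 and q = 0.30 (the two rates of the power calculation) and w assumed:

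- w = 0.05: 0.05 × 0.20 = 0.01
- w = 0.10: 0.10 × 0.20 = 0.02
- w = 0.20: 0.20 × 0.20 = 0.04

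None of these values of w comes from the protocol. The calculation also ignores the planned imputation.

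**5. Room in the sample size.** The plan's figure reproduces: (1.960 + 0.842)² × (0.30 × 0.70 + 0.50 × 0.50) / 0.20² = 90.3, so 91 per group. The design effect of 2 gives 4 × 91 = 364, against 360 stated. The expected 500 × 0.80 = 400 at follow-up leaves 400 − 360 = 40 consumers, or 8% of 500, before the stated requirement is missed. The protocol does not say whether withdrawals for these two reasons are inside the 20% loss.

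**The case against.** The strongest reply is that 6.9 is a loosely worded withdrawal clause and that the rest of the protocol protects the ITT set. Much of this stands. The wording permits withdrawal and does not require it, and no section directs the team to remove anyone. A reader might infer that intervention consumers who do not use the online plan lose follow-up. The protocol does not support that: nowhere does it call missing software or an unused plan a violation, it keeps the foreseeable departures in follow-up (table above), and 8.2 plans subgroups by degree of completion, which presupposes that non-adherers stay in the data. A reader might also infer that hospital use after adverse events is systematically removed. Section 5.3 points the other way for admitted consumers, whose assessment is arranged after discharge.

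It can also be argued that 6.9 means consent withdrawal only, as 6.8 describes the participant deciding and notifying the team. This does not close the gap, because 6.9 lists violation and adverse event separately from the participant's choice.

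Multiple imputation is planned for drop-outs and, more widely in 8.2, for missing survey, practice and merged data. It is a weaker remedy than the records themselves, and it is hard to rely on when removal follows from a deviation or event that may be related to outcome.

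**Conclusion.** The point holds in a limited form. Section 6.9 permits withdrawal for an undefined protocol violation or any adverse event, and then ends data collection. That is inconsistent with the ITT analysis and drop-out definition in 8.2 and with the retention rules elsewhere. The exposure is restricted to consumers classed under those two reasons. Losses through adverse events could fall mainly on the intervention arm because of how section 6.3 identifies them; this assumes that the team would use the permission. The number affected, and so the size of any bias, cannot be derived from the protocol, and the percentages in the working are not estimates. It is worth correcting because the change is small and removes an avoidable source of loss.

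**What to change.** In 6.9, state that only the participant's own withdrawal of consent ends data collection. After a protocol violation, an eligibility deviation found later or an adverse event, the consumer stays in the allocated arm, is still offered the repeat survey, and still has records extracted within the consent given. Record such deviations by arm. Align 6.8 (the question about secondary data), 6.9 (the status codes) and the drop-out definition in 8.2. The change concerns data collection only and leaves decisions about care, and the right to withdraw, as they are.

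The cost is a short rewrite of 6.9 with matching edits in 6.8 and 8.2, a few extra follow-up contacts, and a check that the consent wording covers continued extraction. The consent forms were not available for this review, so that check cannot be skipped.

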7. OUTCOMES AND DATA SOURCES

Table 9 Outcomes and their data sources

Concept	Primary Outcomes	Data source
1 Preventive care	GP-recorded screening of health risks 6-month period post-intervention* (May-October 2023) compared with the 6-month periods: 
 • Pre-intervention (November 2022-April 2023) • In the previous year (May-October 2022) 
*"intervention" = shard care plan in Inca (May-June 2023)
	GP records
	GP-recorded prescription of antihypertensive or lipid lower medications 6-month period post-intervention* (May-October 2023) compared with the 6-month periods: 
 • Pre-intervention (November 2022-April 2023) • In the previous year (May-October 2022) 
*"intervention" = shard care plan in Inca (May-June 2023)
	GP records & HealtheNet
	Consumer-reported advice/referral from GP for smoking cessation, diet and physical activity in last 6 months	Consumer survey

Concept	Secondary Outcomes	Data source
1 Preventive care	GP-recorded care plans: GPNP and Team Care, mental health 6-month period post-intervention* (May-October 2023) compared with the 6-month periods: 
 • Pre-intervention (November 2022-April 2023) • In the previous year (May-October 2022) 
*"intervention" = shard care plan in Inca (May-June 2023)
	GP records
2 Integration of care	Consumer assessment of extent to which providers (MH & GP) are working to a common care plan in last 6 months	Consumer survey
	Provider reported quality of communication between MHSs and GPs in last 6 months	Provider survey and qualitative interviews

Concept	Secondary Outcomes	Data source
3 Health service use	ED use and hospitalisations for primary care preventable conditions and other conditions 6-month period post-intervention* (May-October 2023) compared with the 6-month periods: 
 • Pre-intervention (November 2022-April 2023) • In the previous year (May-October 2022, to check for seasonal effect) 
*"intervention" = shard care plan in Inca (May-June 2023)
	SLHD eMR (Appendix 14), Integrated Care Outcomes Database (ICOD)
	GP visits 6-month period post-intervention* (May-October 2023) compared with the 6-month periods: 
 • Pre-intervention (November 2022-April 2023) • In the previous year (May-October 2022, to check for seasonal effect) 
*"intervention" = shard care plan in Inca (May-June 2023)
	GP records EMR Report (CMH011 Document Audit)
	Number of consumers engaged in Mental Health Shared Care arrangements and applicable outcomes, GP contact details	EMR Reports (AMH Current Clients; AMH Metabolic Monitoring) (Appendix 14),
	Consumer experience of providers (MH & GP) working to a common care plan in last 2 years	Consumer and carer qualitative interviews
4 consumer health risks	Consumer health literacy score in last 6 months	Consumer survey
	Consumer health risk behaviours in las 6 months	
	Consumer diabetes risk score on AUSDRISK in last 6 months***	

Concept	Secondary Outcomes	Data source
5 Cost-consequence and cost-effectiveness	Costs of hospitalisations and other healthcare services avoided 6-month period post-intervention* (May-October 2023) compared with the 6-month periods: 
 • Pre-intervention (November 2022-April 2023) • In the previous year (May-October 2022, to check for seasonal effect) 
*"intervention" = shard care plan in Inca (May-June 2023)
	Hospitalisations data, SLHD Healthcare Use (especially hospitalisations, length of stay, procedures) and Cost data using medical record numbers, Consumer survey, eMR Reports 'AMH Current Clients', 'CMH011 Document Audit', and 'AMH Metabolic Monitoring', SLHD Targeted Activity & Reporting System (STARS)
	Consumer quality of life score on EQ5D-5L in last 6 months	Consumer survey

* See Table 3

** See Table 4

*** See Table 5

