4.2. EXPECTED PARTICIPANT NUMBERS

We aim to recruit 500 consumers and expect 400 to remain in the study at 3-month follow-up (20% loss to follow up). Power calculation: Assuming 20% change in the frequency and quality of primary and preventative care received by participants, a sample size of 91 per group is required to detect a change from 30 to 50% in primary outcomes based on $\alpha = 0.05$, $1-\beta = 0.8$. Assuming a design effect due to clustering of 2, a total sample of 360 is required (180 in each group).

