4.4. ENDPOINTS

PRIMARY ENDPOINTS

Differences between the intervention and comparison groups in changes in the frequency and quality of preventive care from their reported usual shared care to 3-months:

1. Increased % of consumers for whom each health risk is measured and recorded over the preceding 3 months*
2. Increased % consumers who have been vaccinated against influenza over the preceding 3 months
3. Decreased % consumers with high CVD risk who have not received a prescription for either an anti-hypertensive or lipid lowering drug.
4. Increased % consumers who report advice/referral for smoking cessation, diet education and physical activity over the preceding 3 months.

* Health risks are itemised in Table 3.

SECONDARY ENDPOINTS

Differences between the intervention and comparison groups in changes from their reported usual shared care to 3-months:

5. Increased % MHS consumers have a care plan (GPMP and TCA) in last 3 months
6. Increased consumer rating of extent to which providers (MH & GP) are working to a common care plan in the past 3 months
7. Improved quality of communication between MHSs and GPs in last 3 months
8. Reduced number of ED attendances and hospitalisations in last 3 months
9. Increased number of visits to GP in last 3 months
10. Improved consumer experience of providers (MH & GP) working to a common (shared) care plan in the past 3 months (qualitative analysis)
11. Increased scores on Domain 1 (Feeling understood and supported by healthcare providers) and Domain 7 (Navigating the healthcare system) of the Health Literacy Questionnaire
12. Increased score on Patient Activation Measure (PAM-13)
13. Improved diet and physical activity behaviours
14. Reduced Absolute Cardiovascular Disease Risk score **
15. Reduced diabetes risk score using AUSDRISK ***
16. Improved levels of most recently recorded results from health risk screening*
17. Reduced costs of hospitalisations in last 3 months
18. Reduced out of pocket costs of participants
19. Improvements in Quality of Life as assessed by the EQ5D-5L.

* Health risks are itemised in Table 3.

** Information needed for CVD risk score is provided in Table 4

*** Information needed for AUSDRISK score is provided in Table 5.

Table 3 Health risks

Health risks	Units/options	Normal range/goals
Systolic & diastolic blood pressure (BP)	mmHg	<130/85 mm Hg

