Secondary data from GP records, and SLHD eMR data (including hospitalisations, ED visits and ambulatory care records, associated costs, documentation audit report and metabolic report) as well as information from SLHD Targeted Activity & Reporting System (STARS) will be obtained and merged with the consumer survey data within the SLHD by AI [name]/AI [name]. GP records will be used to answer research questions 1 and 2 – quantitative analysis is described above. SLHD's patient data from the eMR (including hospitalisation, ED visits, ambulatory data, documentation audit and metabolic monitoring) as well as information from STARS and cost information will be used to answer research questions 3 and 4. These analyses of the resulting combined and de-identified dataset are described below.

The merged SLHD administrative data (micro-level data) will be from a 6-month period post-intervention (May-October 2023, considering the intervention as having a shared care plan in Inca between May and June 2023) compared with the 6-month periods, a) pre-intervention (November 2022-April 2023) and b) in the previous year (May-October 2022, to check for seasonal effect). The data will be analysed as part of the healthcare cost component (in the larger health economic evaluation).

The healthcare usage (such as hospitalisations, ED visits, ambulatory care and GP care) data will firstly be grouped in a meaningful way e.g., for hospitalisations, summarised by ARDRGs, diagnoses and average length of stay. Costs will be summarised too e.g., for hospitalisation costs, these will be described in terms of main components such as 'Medical', 'Nursing' and 'Allied Health' costs occurring during admissions. We will calculate the total and mean utilisation of healthcare services and costs (and undertake further econometric analyses) for those in the SHAReD intervention, usual care, and combined (SHAReD and comparison) groups. These summary statistics (and later modelled estimates) will be included in the cost component of the economic evaluation.

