9.2 Consumer quantitative interviews

Survey interviews will be conducted with both intervention and comparison consumers at baseline and 3 months after their usual shared care (or 30 June 2023 if they did not have a shared care plan). The interview schedule components and their sources are summarised in Table 9.

Table 10 Sources of questions in the consumer survey

Outcomes	Source of questions
Consumer-reported advice/referral from GP for smoking cessation, diet and physical activity in last 6 months	Questions developed by CPHCE in previous research ^{32,33}
Consumer assessment of extent to which providers (MH & GP) are working to a common care plan in last 6 months	Question developed by CPHCE, informed by research on interprofessional teamworking in primary and community care settings ³⁴
Health literacy (Feeling understood and supported by healthcare providers)	Health Literacy Questionnaire (HLQ) (Domain 1) ³⁵
Current health risk behaviours	Questions developed by CPHCE
Absolute Cardiovascular Disease Risk	Australian Absolute Cardiovascular Disease Risk ³⁷
Diabetes risk	AUSRISK ³⁸
Quality of life	EQ5D-5L ^{28,29}
Costs	Out-of-pocket costs

Accommodation of mental illness: Interviews will be usually conducted by telephone or video conferencing. Carers or support workers will be asked to assist if the participants agree. The interview questions will use plain English and graphic images. Where participants are judged by treating staff to be unable to understand or answer questions remotely the interviews will be conducted in person, with arrangements to ensure the safety of the consumer and research team. In person interviews will be conducted in a location such as health service and respecting social distancing in accordance with the COVID-19 plan of the SLHD. Carers or support workers will be asked to assist if the participant wishes.

The study procedure is flexible allowing interviews to be postponed if the participant is distressed or acutely ill. If participants become distressed during the interview, researchers will provide basic support and inform the care coordinator that the consumer was feeling distressed and might need follow up. If this happens out of hours, the researcher will ask the consumer if there is somebody they should call who can provide support e.g., support worker, GP or carer. If the researcher is concerned about a participant's safety out of hours, they will contact the mental health line [name].

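### The advice/referral primary endpoint has two look-back periods, 3 months in Section 4.4 and 6 months in Tables 9 and 10; the longer one reaches back before the shared-care visit and probably dilutes the contrast

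*Protocol*

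**What the plan says.** Section 4.4 frames the primary endpoints as between-group differences in "changes in the frequency and quality of preventive care from their reported usual shared care to 3-months". Its fourth primary endpoint is "Increased % consumers who report advice/referral for smoking cessation, diet education and physical activity over the preceding 3 months".

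Table 9 (Section 7) lists the same primary outcome, with the consumer survey as its source, as "Consumer-reported advice/referral from GP for smoking cessation, diet and physical activity in last 6 months". Table 10 (Section 9.2), which gives the origin of the survey questions, also uses 6 months.

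On timing, Section 9.2 states: "Survey interviews will be conducted with both intervention and comparison consumers at baseline and 3 months after their usual shared care". For consumers with no shared-care appointment since baseline, the synopsis (Study Procedure) says "they will be invited to participate in the repeated interview three months after 30 June 2023". Section 8.2 dates the intervention by "considering the intervention as having a shared care plan in Inca between May and June 2023".

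The same 3-versus-6-month difference appears for two secondary endpoints. The rating of a common care plan (endpoint 6) has 3 months in Section 4.4 and 6 in Tables 9 and 10. Communication between services (endpoint 7) has 3 months in Section 4.4 and 6 in Table 9.

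**The concern.** A primary endpoint with two definitions lets the choice be made after the data are seen. Whoever writes the analysis from this protocol inherits two outcomes under one name.

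The two periods are also not equally well matched to the design. The interval that Section 4.4 sets runs from shared care to 3 months later, and the survey comes at the end of it. A 6-month question asked then adds about 3 months in which the visit had not yet happened. For a yes/no outcome of any advice, a consumer advised in those earlier months answers yes in either arm whatever happens afterwards, and so cannot contribute to a difference. The risk is a weakened contrast, and possibly a false null, on a primary endpoint.

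**Working it through.** **Inputs.** Section 4.2 gives 30% versus 50%, 91 per group, alpha 0.05, power 0.80, a design effect of 2, a requirement of 180 per group, and 400 consumers expected at follow-up. Sidedness is not stated; two-sided is assumed.

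**The plan's own figure.** The plan says "a sample size of 91 per group is required to detect a change from 30 to 50% in primary outcomes". With unpooled variance:

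n = (1.960 + 0.842)² × (0.3 × 0.7 + 0.5 × 0.5) / 0.20² = 90.3, so 91 per group. This reproduces.

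Doubling gives 182 per group and 364 in total, against 180 and 360 stated; the gap is rounding. Taking the design effect of 2 as given, the effective size is 180/2 = 90 per arm at the required sample, or 200/2 = 100 per arm at the 400 expected.

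**Power formula**, with n the effective size per arm, d the difference and p̄ the mean of the two proportions:

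power = Φ{ [d − 1.96 √(2p̄(1 − p̄)/n)] / √[(p₁(1 − p₁) + p₂(1 − p₂))/n] }

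For 30% versus 50% this gives 0.79 at n = 90 and 0.83 at n = 100.

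**Share of the look-back before the visit.** Survey at visit + 3 months, look-back 6 months: (6 − 3)/6 = 50%.

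**Effect on the contrast.** Let q be the chance of advice in the 3 pre-visit months, equal in both arms, and let c and t be the chances in the 3 post-visit months (comparison, intervention). If the two halves are independent:

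difference over 6 months = [1 − (1 − q)(1 − t)] − [1 − (1 − q)(1 − c)] = (1 − q)(t − c)

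So the share kept is 1 − q, which is not one half in general. It is 90% at q = 0.10, 70% at q = 0.30 and 50% at q = 0.50.

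The protocol does not say what period the 30% and 50% cover, so three cases are shown for the 6-month question:

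| Assumption | Comparison | Intervention | Difference | Power, n = 90 | Power, n = 100 |
|---|---|---|---|---|---|
| Same people advised in both halves | 30% | 50% | 20 points | 0.79 | 0.83 |
| 30%/50% are 3-month rates, halves independent | 1 − 0.7² = 51% | 1 − 0.7 × 0.5 = 65% | 14 points | 0.48 | 0.52 |
| 30%/50% are 6-month rates, constant rate | 30% | 1 − √(0.7 × 0.5) = 40.8% | 10.8 points | 0.33 | 0.36 |

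The losses against the planned 20 points are 0%, 6/20 = 30%, and 9.2/20 = 46%.

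**What a 3-month question would give.** In the second case it restores 30% versus 50%, with power 0.79 to 0.83. In the third it gives 1 − √0.7 = 16.3% versus 1 − √0.5 = 29.3%, a difference of 13.0 points with power 0.54 to 0.59. So in the third case the step from 20 to 13.0 points comes from having only 3 exposed months, and only the step from 13.0 to 10.8 comes from the pre-visit months. The shorter question still has the higher power there, partly because lower percentages carry less variance.

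**The case against.** A reader might infer that because half the window is before the visit, the effect is halved. The documents do not support that. The loss comes near one half only if the 30% and 50% are 6-month rates arising at a constant rate, or if the pre-visit 3-month rate is itself near 50%. The protocol states neither.

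The constant-rate case may also fit the design poorly. Section 6.2 has care-plan tasks completed at GP visits. If advice clusters at the shared-care visit, the earlier months add little: with q = 0.10 and post-visit rates of 30% and 50%, the 6-month contrast is 37% versus 55%, keeping 18 points. Section 6.2 also allows mental health staff to create the plan before the first GP visit, so exposure can begin somewhat earlier. Consumers with no appointment have no visit to split their window, which runs from about the end of March to the end of September 2023. All of this stands, and it is why only a range is given.

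The tables list outcomes and question sources; the questionnaire (Appendix 3) is not shown. Table 9 attaches the same 6-month phrase to the AUSDRISK score, which includes age, country of birth and family history, so the phrase may be a loose label. That also stands: the question actually asked cannot be checked here. It leaves the contradiction on paper intact.

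The version 11 change to 6-month periods does not settle the matter. As logged, it concerns the GP audit and HealtheNet data, not the consumer survey.

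Finally, the look-back is stated alike for both arms. The harm shown is ambiguity and probable dilution; bias in favour of one arm does not follow from it.

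**Conclusion.** The contradiction is established: one primary endpoint has a 3-month and a 6-month definition in current text. For consumers with a visit who are surveyed on schedule, the 6-month version is about half pre-visit. If pre-visit rates are equal across arms and later advice is no less frequent under the intervention among those already advised, the added months cannot enlarge the absolute difference; they leave it unchanged or shrink it.

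The size is not fixed by the protocol. It runs from no loss, through 14 of 20 points kept, to 10.8 of 20 kept. These rest on the assumed period for the 30% and 50%, on the dependence between the two halves, and on the plan's design effect of 2. The power figures illustrate the effect of the look-back and should not be read as the trial's power.

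For endpoints 6 and 7 only the conflict is asserted. They concern ratings of joint planning and quality of communication, and the yes/no calculation does not carry over to them.

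This should be fixed; it does not by itself invalidate the trial.

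**What to change.** Use one look-back for endpoints 4, 6 and 7 in Section 4.4, Tables 9 and 10 and the questionnaires, identical in both arms and matched to the interval that Section 4.4 already sets. For consumers, anchor it to the event, for example: *since your shared care visit (about 3 months ago)*. A bare 3-month question puts the visit at the edge of the window, and Section 9.2 allows interviews to be postponed, so a late interview would drop the visit. For consumers with no appointment, use the 3 months since 30 June 2023.

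State in Sections 4.2 and 8.1 which period the 30% and 50% refer to.

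Version 11 is dated 18 October 2023, so some follow-up surveys may already be done. Where follow-up was asked over 6 months, report it as a 6-month outcome and interpret it as possibly diluted. Where baseline used a different period from follow-up, enter it as a covariate and do not subtract it.

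The cost is a wording change and an ethics notification. The downside is a lower percentage reporting advice in both arms than over 6 months.
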